2. STUDY OBJECTIVES

2.1 Primary objective

Table 1 Primary objective

Primary objective	Primary outcome variables
To investigate the pharmacokinetics of olaparib after a single oral dose of 300 mg to patients with advanced solid tumours and mild or moderate hepatic impairment compared to those with normal hepatic function.	Maximum plasma concentration (C_{max}), area under the plasma concentration time curve from zero to the last measurable time point (AUC_{0-t}), area under the plasma concentration time curve from zero to infinity (AUC), time to reach maximum plasma concentration (t_{max}), terminal half-life ($t_{1/2}$), apparent clearance following oral administration (CL/F), apparent volume of distribution (V_z/F) and terminal rate constant (λ_z).

2.2 Secondary objectives

Table 2 Secondary objective

Secondary objective	Secondary outcome variables
To investigate the safety and tolerability of single and multiple oral doses of olaparib in advanced solid tumour patients with mild or moderate hepatic impairment and in those with normal hepatic function.	Assessment of AEs, graded by CTCAE (v4.0), physical examination, vital signs (including BP and pulse) standard 12-lead ECG and evaluation of laboratory parameters (clinical chemistry, haematology and urinalysis).

BP blood pressure; CTCAE Common Terminology Criteria for Adverse Events; ECG electrocardiogram

2.3 Exploratory objectives

Table 3 Exploratory objective

Exploratory objective	Exploratory outcome variables
To explore changes in protein binding of olaparib and the subsequent effects on its PK in patients with varying degrees of hepatic function.	In Part A, Plasma protein binding at 1 hour after dosing, used to calculate free C_{max} (C_{max} of unbound olaparib), free AUC (AUC of unbound olaparib) and unbound CL/F (CL/F of unbound olaparib).

3. STUDY PLAN AND PROCEDURES

This Clinical Study Protocol has been subject to a peer review according to AstraZeneca standard procedures.

3.1 Overall study design and flow chart

This is a 2-part study in patients with advanced solid tumours. Part A will investigate the PK of olaparib in patients with mild or moderate hepatic impairment compared to patients with normal hepatic function; Part B will allow patients continued access to olaparib after the PK phase and will provide additional safety data.

Approximately 30 patients are planned to be enrolled from approximately 20 sites in Europe, with the possibility of sites in North America and Asia, with at least 24 evaluable patients required to complete Part A (8 patients with normal hepatic function, 8 with mild hepatic impairment [Child-Pugh A] and 8 with moderate hepatic impairment [Child-Pugh B]). An evaluable patient is defined as a patient having full PK sampling to 96 hours post-dose of olaparib. Groups will be recruited so that, if possible, at least 3 patients of each sex are in each group. Patients with normal hepatic function and mild hepatic impairment will be recruited before those with moderate hepatic impairment. At least 3 months of safety data (and PK data if available) from at least 3 patients with mild hepatic impairment will be reviewed before recruiting patients with moderate hepatic impairment into the study, first in Part A and then in Part B. If the safety, tolerability and PK data from the 3 patients with mild hepatic impairment dosed continuously with olaparib for 3 months raises safety concerns for the continuous dosing of patients with moderate hepatic impairment, then patients with moderate hepatic impairment will not enter the study.

Part A is an open-label, parallel group, PK study comparing patients with mild or moderate hepatic impairment to patients with normal hepatic function. Each patient will receive a single oral dose of olaparib 300 mg (given via the tablet formulation). Where possible, patients will check into the clinic on Day -1, the evening prior to dosing (Day 1), remain resident until 24 hours after the dose of olaparib (Day 2), and then return to the clinic for assessments on Day 3 (48 hours), Day 4 (72 hours) and Day 5 (96 hours). The overall study plan for Part A of the study is provided in [Table 4](#).

Blood samples for the determination of olaparib will be collected during Part A. Full details of the blood PK sampling times are provided in [Table 5](#).

On completion of Part A, patients may be entered into Part B and continue to take olaparib tablets (300 mg bd) if they and the investigator agree that this is appropriate, providing the baseline safety assessments for Part B are in accordance with the study inclusion and exclusion criteria and patients continue to meet the criteria for mild or moderate hepatic impairment or normal hepatic function.

Patients must start Part B within 2 weeks (minimum 5 days, maximum 14 days) of dosing in Part A. Patients will have weekly clinic visits for the first 4 weeks; thereafter visits will be every 4 weeks. Assessments will be conducted as shown in [Table 6](#). Part B will be of 12 months' duration from the date the last patient enters this part of the study.

During and after Part B, patients may continue to take olaparib, if they and the investigator deem it appropriate, until such time as their disease progresses, the investigator believes they are no longer deriving clinical benefit, or they stop taking olaparib for any other reason. After the end of Part B (12 months after the last patient entered Part B), patients will be seen as per their normal routine clinical schedule and no clinical data will be collected, other than serious adverse events (SAEs).

Patients will return to the clinic for follow-up assessments either 30 days (± 7 days) after their last dose in the last treatment period in Part A or 30 days (± 7 days) after discontinuation of olaparib in Part B. If a patient discontinues investigational product (IP) during Part B, they will also attend a study treatment discontinuation visit.

A flow chart of Part A of the study is illustrated in [Figure 1](#).

Figure 1 Study flow chart (Part A)

[figure not shown]

Table 4 Study plan – Part A (PK study)

Assessments	Screening	Treatment Period						Follow Up ^a
		1	2	3	4	5	100	
Visits	1	2	3	4	5	100		
Day ^b	-28 to -2 days before dosing	-1 ^b	1	2	3	4	5	30 (±7) days after last dose
Resident in clinic		<----->						
Outpatient visits	X				X	X	X	X
Written informed consent	X							
Demography	X							
Medical/surgical history	X							
Prior and concomitant meds	X	X	X	X	X	X	X	X
Inclusion/exclusion criteria including classification of hepatic function	X	X	X					
Germline BRCA status ^c	X							
ECOG performance status	X							
Height and weight	X							
Physical examination	X	X						X
Vital signs (BP/pulse)	X		X ^d	X	X			X
Body temperature	X		X					
Resting standard 12-lead ECG	X		X ^d		X			X
HBV and HCV Serology ^e	X							
Haematology/coagulation ^f /biochemistry	X	X			X			X
Urinalysis ^g	X	X			X			X
Serum/urine pregnancy test ^h	X		X					
Olaparib administration			X					
Protein binding sample ⁱ			X					
Olaparib PK blood sampling ^j			X	X	X	X	X	
Adverse events ^k	X	X	X	X	X	X	X	X

BP blood pressure; BRCA breast cancer gene; ECG electrocardiogram; ECOG Eastern Cooperative Oncology Group; HBV hepatitis B virus; HCV hepatitis C virus; HR heart rate; PK pharmacokinetics

^a For patients who withdraw from the study prematurely or do not participate in Part B

- b There is no Day 0. Day 1 is the day of dosing; Day -1 is the day before dosing. All Day -1 procedures must be performed on Day -1 or pre-dose on Day 1. If the patient has been screened within 48 hours of Day 1, safety laboratory tests (haematology, coagulation, biochemistry and urinalysis) do not need to be repeated.
- c Germline BRCA status to be collected on CRF, if known. If known, record whether patient is +ve or -ve for mutation. If +ve, record sequence.
- d Pre-dose and 4 hours post-dose.
- e Includes HBsAg (hepatitis B surface antigen), anti-HBs (anti-hepatitis B surface antigen), anti-HBc (anti-hepatitis B core antigen) and anti-HCV
- f Coagulation (aPTT and INR) will be performed at baseline and if clinically indicated. For patients taking warfarin reference Section 5.6.3.
- g Protein, blood, glucose and bilirubin.
- h Pre-menopausal women of childbearing potential must have a negative urine or serum pregnancy test within 28 days prior to starting treatment and a confirmatory test before dosing on Day 1. In the event of a suspected pregnancy during the study, the test should be repeated and, if positive, the patient discontinued from study treatment immediately.
- i Blood sample collected for protein binding analysis at 1 hour post-dose (see Table 5).
- j Olaparib PK samples will be collected at pre-dose, 0.25, 0.5, 1, 1.5, 2, 3, 4, 6, 8, 12, 24, 48, 72 and 96 hours after olaparib dosing (see Table 5).
- k If a patient withdraws for any reason, any ongoing study-related toxicity or SAE at discontinuation must be monitored until resolution. After discontinuation from treatment, patients must be followed up for any new AEs for 30 calendar days after last dose of IP. All existing and any new AEs occurring during the 30-day period must be recorded and followed to resolution if possible.

Table 5 Pharmacokinetic sampling – Part A (PK study)

Day	Time (h)	Dose	PK blood sample ^a	Protein binding sample ^b
1	Pre-dose		X	
	0	X		
	0.25		X	
	0.5		X	
	1		X	X
	1.5		X	
	2		X	
	3		X	
	4		X	
	6		X	
	8		X	
	12		X	
	2	24		X
3	48		X	
4	72		X	
5	96		X	

PK pharmacokinetic

^a Venous blood samples (4 mL) for determination of olaparib in plasma.

^b Protein binding sample (3 mL) to determine the free fraction of olaparib in plasma

Table 6 Study plan – Part B (continued access to olaparib)

Visit Number	6 ^a	7	8	9	10	Subsequent on-treatment visits every 4 weeks ^b Visit 11 onwards	Study treatment discontinued	Follow-up 30 (±7) days after last dose of study medication
Day	1 ^a	8	15	22	29	Day 1 of next visit period (Equals Day 57 [Week 9] then Day 85 [Week 13], etc)		
Visit window		±3d	±3d	±3d	±3d	±7d	±7d	±7d
Physical examination ^c	X							
Vital signs (BP, pulse, temperature)	X	X	X	X	X	X	X	X
ECOG performance status	X							
Resting standard 12-lead ECG	X					X		X
Haematology ^d /clinical chemistry	X ^d	X	X	X	X ^d	X ^d	X ^d	X ^d
Urinalysis ^e	X	X	X	X	X	X	X	X
Adverse events	X	X	X	X	X	X	X	X
Previous and concomitant medications	X	X	X	X	X	X	X	X
Olaparib dispensed/returned ^f	X				X ^e	X ^e	X	

BP blood pressure; ECG electrocardiogram; ECOG Eastern Cooperative Oncology Group

Note: A pregnancy test will be conducted only in the event of a suspected pregnancy during the study.

^a Baseline safety assessments must be in accordance with the study inclusion and exclusion criteria

^b Visit to take place on Day 1 of a 4 week (28 day) visit period. Visits will continue for 12 months from the date the last patient enters Part B.

^c After baseline, it is not necessary to record any physical examination details on the CRF; any clinically significant changes should be recorded as AEs.

^d Haematology assessment to include prothrombin time for patients with mild or moderate hepatic impairment at every visit
Additional haematology assessments will be performed on Day 1, then monthly for 6 months, at discontinuation, and at the 30-day follow-up visit (see Section 6.4.5).

^e Protein, blood, glucose and bilirubin. Urinalysis to be conducted at every visit for patients with hepatic impairment. After baseline, urinalysis is only required for patients with normal hepatic function if clinically indicated.

^f Sufficient study treatment should be dispensed for at least each treatment period plus overage; however additional treatment can be dispensed to patients to last longer in accordance with local practice.

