1.1.2 Toxicology and safety pharmacology summary

Olaparib has been tested in a standard range of safety pharmacology studies, eg, dog cardiovascular and respiratory function tests, and the rat Irwin test. There were no noticeable effects on the cardiovascular or respiratory parameters in the anaesthetised dog or any behavioural, autonomic, or motor effects in the rat at the doses studied.

Rodent and dog toxicology studies have indicated that the primary target organ of toxicity is the bone marrow with recovery seen following withdrawal of olaparib. Ex vivo studies have confirmed that olaparib is cytotoxic to human bone marrow cells.

Olaparib was not mutagenic in the Ames test but was clastogenic in the Chinese hamster ovary (CHO) chromosome aberration test in vitro. When dosed orally, olaparib also induced micronuclei in the bone marrow of rats. This profile is consistent with the potential for genotoxicity in man.

Reproductive toxicology data indicate that olaparib can have adverse effects on embryofetal survival and development at dose levels that do not induce significant maternal toxicity.

Further information can be found in the current version of the olaparib IB.

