 - Nodules >1 cm found on ultrasound screening of a cirrhotic liver should be investigated further with either 4-phase multi-detector CT scan or dynamic contrast enhanced MRI. If the appearances are typical of HCC (ie, hyper-vascular in the arterial phase with washout in the portal venous or delayed phase), the lesion should be treated as HCC. If the findings are not characteristic or the vascular profile is not typical, a second contrast-enhanced study with the other imaging modality should be performed, or the lesion should be biopsied (level II) ([Bruix et al 2011](#)).

8. Normal organ and bone marrow function measured within 28 days prior to administration of IP as defined below:
 - Haemoglobin ≥ 9.0 g/dL, with no blood transfusions in the previous 28 days
 - Absolute neutrophil count (ANC) $\geq 1.5 \times 10^9/L$
 - White blood cells (WBC) $> 3 \times 10^9/L$
 - Platelet count $\geq 75 \times 10^9/L$
 - Serum creatinine ≤ 1.5 x institutional ULN
9. Calculated serum creatinine clearance > 50 mL/min (using Cockcroft-Gault formula or by 24-hour urine collection)
10. Eastern Cooperative Oncology Group (ECOG) performance status ≤ 2 .
11. Patients must have a life expectancy ≥ 8 weeks.
12. Evidence of non childbearing status for women of childbearing potential, or postmenopausal status: negative urine or serum pregnancy test within 28 days of study treatment, confirmed prior to treatment on Day 1 of the first treatment period in Part A

Postmenopausal is defined as:
 - Amenorrheic for 1 year or more following cessation of exogenous hormonal treatments
 - Luteinising hormone and follicle-stimulating hormone levels in the postmenopausal range for women under 50 years of age
 - Radiation-induced oophorectomy with last menses > 1 year ago
 - Chemotherapy-induced menopause with > 1 year interval since last menses
 - Surgical sterilisation (bilateral oophorectomy or hysterectomy).
13. Patients are willing and able to comply with the protocol for the duration of the study including undergoing treatment and scheduled visits and examinations.
14. Patients must be on a stable concomitant medication regimen (with the exception of electrolyte supplements), defined as no changes in medication or in dose within 2 weeks prior to start of olaparib dosing, except for bisphosphonates, denosumab and corticosteroids, which should be stable for at least 4 weeks prior to start of olaparib dosing.

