6.4.5 Laboratory safety assessment

Blood and urine samples for determination of clinical chemistry, haematology, coagulation, and urinalysis parameters will be taken at the times given in the study plans ([Table 4](#) and [Table 6](#)).

The following laboratory variables will be measured:

- Full haematology assessments for safety (Hb, red blood cells [RBC], platelets, mean corpuscular volume [MCV], mean corpuscular Hb concentration [MCHC], mean corpuscular Hb [MCH], WBC, differential white cell count and ANC should be performed in accordance with the study plans and when clinically indicated. Coagulation (aPTT and INR) will be performed at baseline and if clinically indicated. For patients taking warfarin reference [Section 5.6.3](#).
- To investigate increases in MCV with olaparib treatment, additional haematology assessments of vitamin B12, folate, red blood cell folate and thyroid stimulating hormone (TSH) will be performed during Part B only. If available from the complete blood count report, the reticulocyte count and red cell distribution width should also be recorded. These additional assessments will be performed on Day 1, then monthly for the first 6 months, at discontinuation, and at the 30-day follow-up visit.
- Biochemistry assessments for safety (sodium, potassium, calcium, magnesium, glucose, creatinine, total bilirubin, gamma glutamyltransferase [GGT], alkaline phosphatase [ALP], AST, ALT, urea or blood urea nitrogen [BUN], total protein, albumin and lactate dehydrogenase [LDH]) will be performed.
- Urinalysis: protein, blood, glucose and bilirubin

In Part A, 2 pregnancy tests on blood or urine samples will be performed for pre-menopausal women of childbearing potential, one within 28 days prior to the start of IP and the other on Day 1 of the study prior to commencing treatment. In Part B, a pregnancy test will be conducted at baseline but should be repeated in the event of a suspected pregnancy during the study. Tests will be performed by the hospital's local laboratory. If results are positive, the patient is ineligible/must be discontinued from the study.

Routine urinalysis should be performed if clinically indicated. Microscopic analysis should be performed by the hospital's local laboratory if required. These tests will be performed by the hospital's local laboratory. Additional analyses may be performed if clinically indicated.

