1. ACCEPTABLE BIRTH CONTROL METHODS

Olaparib is regarded as a compound with medium/high foetal risk.

Women of childbearing potential and their partners, who are sexually active, must agree to the use of 2 highly effective forms of contraception in combination [as listed below], throughout the period of taking study treatment and for at least 1 month after last dose of study drug(s), or they must totally/truly abstain from any form of sexual intercourse (see below).

Male patients and their partners, who are sexually active and of childbearing potential, must agree to the use of 2 highly effective forms of contraception in combination [as listed below], throughout the period of taking study treatment and for 3 months after last dose of study drug(s) due to the unknown effects of the study drug on the sperm, or they must totally/truly abstain from any form of sexual intercourse (see below). Male patients should not donate sperm throughout the period of taking study treatment and for 3 months following the last dose of study drug(s).

Acceptable Non-hormonal birth control methods include:

- Total sexual abstinence. Abstinence must continue for the total duration of study treatment and for at least 1 month after the last dose for women of childbearing potential and their partners and for 3 months after last dose for male patients. Periodic abstinence (eg, calendar ovulation, symptothermal post ovulation methods) and withdrawal are not acceptable methods of contraception.
- Vasectomised sexual partner PLUS male condom. With participant assurance that partner received post-vasectomy confirmation of azoospermia.
- Tubal occlusion PLUS male condom
- IUD PLUS male condom. Provided coils are copper-banded

Acceptable hormonal methods:

- Normal and low dose combined oral pills PLUS male condom
- Cerazette (desogestrel) PLUS male condom. Cerazette is currently the only highly efficacious progesterone based pill.
- Hormonal shot or injection (eg., Depo-Provera) PLUS male condom
- Etonogestrel implants (eg, Implanon, Norplant) PLUS male condom
- Norelgestromin / EE transdermal system PLUS male condom
- Intrauterine system [IUS] device (eg, levonorgestrel releasing IUS -Mirena®) PLUS male condom
- Intravaginal device (eg, EE and etonogestrel) PLUS male condom

Clinical Study Protocol Appendix G

Drug Substance	Olaparib (AZD2281, KU-0059436)
Study Code	D0816C00005
Edition Number	1.0
Date	03 June 2013

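### Table 6 allows a Part B pregnancy test only on suspicion, while Section 6.4.5 requires one at Part B baseline, so a site following the schedule starts continuous dosing without it

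*Protocol*

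**What the plan says.** Section 3.1 of the protocol directs that Part B assessments follow Table 6. That table has no pregnancy-test row at any visit, and its note states: "A pregnancy test will be conducted only in the event of a suspected pregnancy during the study". Footnote a, attached to Visit 6 (Part B Day 1), adds: "Baseline safety assessments must be in accordance with the study inclusion and exclusion criteria".

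Section 6.4.5 sets two tests for Part A and then continues: "In Part B, a pregnancy test will be conducted at baseline but should be repeated in the event of a suspected pregnancy". A positive result makes the patient ineligible or leads to discontinuation.

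Inclusion criterion 12 in Section 4.1 asks for a negative test within 28 days of study treatment, "confirmed prior to treatment on Day 1 of the first treatment period in Part A". On the interval between the two parts, Section 3.1 says: "Patients must start Part B within 2 weeks (minimum 5 days, maximum 14 days) of dosing in Part A".

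**The concern.** The schedule and the laboratory section give opposite instructions for the same visit. Sites commonly work from the schedule of assessments, and this schedule both omits the test and restricts testing to suspected pregnancies. A woman of childbearing potential could then move from one supervised dose to continuous self-administered dosing without the check Section 6.4.5 intends. A pregnancy arising after the Part A Day 1 test would be looked for only if someone suspected it.

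The protocol gives its own reasons to care. Section 1.1.2 reports that "olaparib can have adverse effects on embryofetal survival and development at dose levels that do not induce significant maternal toxicity", and Appendix F states: "Olaparib is regarded as a compound with medium/high foetal risk". Whichever text a site follows, it also departs from the other.

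**Working it through.** No sample size, power or error-rate figure is involved. The check compares the texts and works out one time interval.

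**1. Do the two instructions concern the same visit?** Yes. The Section 6.4.5 sentence is expressly about Part B and follows a separate sentence on Part A testing. Section 3.1 refers to baseline safety assessments for Part B, and Table 6 footnote a places them at Visit 6, Day 1. Baseline in Section 6.4.5 is therefore Part B entry.

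**2. Side by side**

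| | Table 6 and its note | Section 6.4.5 |
|---|---|---|
| Test at Part B baseline | No row; excluded by the restriction to suspected cases | Required |
| Test on suspicion | Yes | Yes |
| Routine test at later Part B visits | None | None |

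The conflict is confined to the first row, and both entries cannot be followed.

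**3. Does other text resolve it?**

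- *Deferral to the study plans.* Section 6.4.5 says samples for "clinical chemistry, haematology, coagulation, and urinalysis parameters will be taken at the times given in the study plans". Pregnancy tests are not in that list, so the sentence does not hand their timing to Table 6.
- *Table 6 footnote d.* It refers the reader to Section 6.4.5, but only for the additional haematology assessments.
- *Table 6 footnote a.* It re-applies the eligibility criteria. The relevant one is criterion 12, whose confirmatory test is tied to Day 1 of Part A.
- *Precedence.* The protocol has no rule ranking the tables against the text on this point.

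**4. Can the Part A result satisfy criterion 12 at Part B entry?**

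- The last mandated test is on the day of the Part A dose, before dosing (Table 4, footnote h).
- Part B starts 5 to 14 days after that dose (Section 3.1).
- The age of the result at Part B entry is therefore 5 to 14 days. Since 14 < 28, criterion 12 is met without a new test.

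**5. How many women?** Section 3.1 aims, where possible, for at least 3 patients of each sex in each of 3 groups, among about 30 enrolled. If that aim is met, the minimum is 3 × 3 = 9 women and the maximum is 30 − (3 × 3) = 21. The protocol does not say how many are of childbearing potential or enter Part B, so the number affected is an assumption, anywhere from 0 to 21.

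**6. Exposure in context.** From Day 1 to Day 28 of Part B a patient takes 28 × 2 = 56 doses if dosing is uninterrupted, against one dose in Part A. This shows how the two parts differ. It does not measure the conflict, because neither text schedules a routine test after baseline.

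**The case against.** The best case on the other side is that this is an editing slip with little consequence. Table 4 footnote h uses similar wording about suspected pregnancy for repeat tests on top of scheduled ones, so the Table 6 note may have been meant only for visits after baseline. Table 6 is not exhaustive in any case: Section 6.4.6 adds physical examinations at every Part B visit that the grid does not show. Sites are bound by Section 6.4.5 too, and some will read it and test. Two tests precede the first dose, two highly effective contraceptive methods must be used together throughout treatment, and a suspected pregnancy triggers a test. What is lost is one repeat test 5 to 14 days after a negative one.

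Most of this stands, and it limits the severity. It does not remove the conflict: the note excludes a baseline test in terms, and the row is missing. Contraception is not a complete answer either. Appendix F accepts hormonal methods with a condom, while Section 5.6.2.2 warns that olaparib may make hormonal contraceptives less effective. By contrast, Table 4 gives the single-dose part an explicit pregnancy-test row.

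**Conclusion.** The concern holds. Table 6 and Section 6.4.5 contradict each other on pregnancy testing at Part B entry, and no other provision reconciles them. The size is best expressed as the age of the last mandated negative test when continuous dosing begins: 5 to 14 days under Table 6, against a new baseline test under Section 6.4.5. It affects only women of childbearing potential who enter Part B, a number the protocol does not give. The consequence arises at sites that follow the schedule; a site that acts on Section 6.4.5 would test.

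The expected harm is small, and PK sampling, sample size and the primary analysis are unaffected. It should still be corrected, because it concerns a safety check before continuous dosing with a drug the protocol regards as a foetal hazard.

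**What to change.** Keep the Section 6.4.5 instruction and bring Table 6 into line with it:

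- Add a row for a serum or urine pregnancy test in women of childbearing potential, marked at Visit 6 (Part B Day 1, before dosing).
- Replace the note with: *Women of childbearing potential will be tested at Visit 6 before the first Part B dose, and again whenever pregnancy is suspected.* The restriction to suspected cases goes.

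The cost is a text amendment to one table and one inexpensive test for each woman of childbearing potential entering Part B (at most 21 if the sex-balance aim is met). Section 6.4.5 already requires that test. PK sampling, sample size and analysis do not change.
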